
Nudges and Incentives to Enhance the Opioid Treatment Workforce

Study Objective(s)	Aim 1: To estimate the influence of informational nudges on the engagement of primary care providers in an opioid treatment learning collaborative to address the opioid overdose crisis. Aim 2: To estimate the influence of financial incentives on the participation intensity of primary care providers in an opioid treatment learning collaborative to address the opioid overdose crisis.
Study Design	The study is designed to be implemented in two phases. Phase 1 is the recruitment phase. Providers will be randomized to receive recruitment letters and emails from 1 of 4 conditions. Randomization for this phase will occur at the practice level, as determined by provider address. Participants that contact the study team and enroll in the study will begin Phase 2 of the study. In Phase 2 of the study participants will be randomly assigned to rewards for participation in ECHO MAT learning collaborative. Their participation in the learning collaborative will be tracked. Phase 2 of the study is a pilot.
Subject Population	Inclusion Criteria
key criteria for Inclusion and Exclusion:	
1. Licensed practicing Primary Care Provider (MD, DO, PA, NP)2. Currently practicing in NC, not currently participating in ECHO MAT Exclusion Criteria 
1. Another member of the same practice is already enrolled in the study (one provider per practice in Phase 2)2. Active participation in The University of North Carolina at Chapel Hill (UNC) ECHO Collaborative at beginning of study
Number of Subjects	Up to 80 to achieve at least 20 in each reimbursement arm
Study Duration	Each subject's participation will last six months with the exception of participants who had not completed as of 3/9/2020 whose participation was extended by 3 months due to decreased learning collaborative sessions resulting from COVID-19. The entire study is expected to last up to two years
Study Phases	(1) Recruitment : recruitment materials (letters or emails) sent once randomized to 1 of 4 conditions. Once participant enrolls, then
Screening	
Study Treatment	

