Follow-Up	(2) Randomization to 1 of 3 study arms: enrolled participants are re-randomized to 1 of 3 levels of reimbursement to estimate the influence of financial incentives in participation in learning collaboratives to address the opioid overdose crisis. Participation in learning collaboratives over 6 months will be

Nudges and Incentives to Enhance the Opioid Treatment Workforce

tracked. Participation in learning collaboratives will be tracked over 9 months for participants who did not complete as of 3/9/2020 due to the COVID-19 pandemic.

Safety Evaluations	The risk to participants is minimal.
Statistical and Analytic Plan	
In Aim 1, we anticipate starting with a random selection of 600 providers from the list of eligible NC providers generated from the NPI Registry, limiting to primary care providers identified through taxonomy codes, which gives more than 90% power to detect a ten percentage point difference in the binary outcome, response to study recruitment. We will use binary models (logit, linear probability models) to examine response to recruitment as a function of study arm, controlling for provider type and county fixed effects.
 
For Aim 2, we will randomly recruit up to 80 providers as needed to have at least 20 providers per arm enrollees for this phase of the pilot (20 providers per arm). The outcome to be monitored for Aim 2 is the number of ECHO sessions attended in the 6 months following randomization. Because this is a pilot study, the sample size is not powered for the primary outcome, number of ECHO clinics attended. We will conduct a negative binomial or other count data model (depending on statistical tests) of the number of sessions as a function of financial incentive arm to estimate the effect of financial incentives on participation.

DATA AND SAFETY MONITORING PLAN	The risk to participants is minimal, and this does not meet the definition of a clinical trial, thus there is no data safety monitoring plan.

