Phase 1: Primary care providers will be randomized by practice to 1 of 4 study arms. Computerized randomization will assign practices to study arms, practices and primary care providers will have an equal chance of being randomized to each study arm.

Phase 2: Eligible participants will be randomized to the Phase 2 study arm upon enrollment in the study. Randomization will be assigned using a predetermined randomly ordered list of study condition assignments. Upon enrolling in the study, the participants will be assigned to the condition that is next on the list. Participants will have an equal chance of being randomized to each study arm.

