3.4 Study Population

Inclusion Criteria

1. Licensed practicing Primary Care Provider (MD, DO, PA, NP)
2. Currently practicing in NC, not currently participating in ECHO MAT

Exclusion Criteria

1. Another member of the same practice is already enrolled in the study (one provider per practice in Phase 2)
2. Active participation in The University of North Carolina at Chapel Hill (UNC) ECHO Collaborative at beginning of study

4 STUDY PROCEDURES (what will be done)

Once a provider is enrolled a schedule of weekly online live UNC ECHO clinic sessions will be sent from the UNC ECHO study team. Attendance is noted at each session and a summary of the prior months' attendance record is sent to the Principal Investigator monthly, indicating the number of hours spent in training and the reimbursement for those sessions. The appropriate dollar amount will be paid to the participant through a reloadable Visa gift card.

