6 STATISTICAL CONSIDERATIONS

6.1 Statistical Methods

In Aim 1, we anticipate starting with a random selection of 600 providers from the list of eligible NC providers received from the NC Board of Medicine and NC Nursing Board, limiting to primary care providers identified as primary care through their provider type, which gives more than 90% power to detect a ten percentage point difference in the binary outcome, response to study recruitment. We will use binary models (logit, linear probability models) to examine response to recruitment as a function of study arm, controlling for provider type and county fixed effects.

For Aim 2, we will randomly recruit at least 60 enrollees (and up to 80 to enroll at least 20 providers per arm of this phase). The outcome to be monitored for Aim 2 is the number of ECHO sessions attended in the 6 months following randomization. Because this is a pilot study, the sample size is not powered for the primary outcome, number of ECHO clinics attended. We will conduct a negative binomial or other count data model (depending on statistical tests) of the number of sessions as a function of financial incentive arm to estimate the effect of financial incentives on participation.

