11 RECRUITMENT STRATEGY

PCPs will be identified from provider lists obtained through the NC Medical Board for physicians and physician assistants and the NC Board of Nursing for nurse practitioners. We will also use the DATA-2000 database of providers to help us identify PCPs who do not have waivers. Providers who are prescribing to Medicaid beneficiaries will be determined from NC Medicaid claims data, which is in use for the ECHO MAT study, and has been IRB approved for re-use for the ECHO Nudges study. We will use the list of providers currently participating in ECHO MAT, available to study investigators, to exclude the providers currently participating in ECHO (n=24). Once the denominator of eligible providers has been determined, the ECHO Nudges study team will randomly select providers in groups of 600 to randomize for pro-social or recruitment as usual invitations to participate in ECHO Nudges (and therefore ECHO MAT). From the group who decide to participate (outcome for Aim 1), we will re-randomize to one of the three arms of financial incentives. Effort to recruit providers for the Aim 2 analysis will follow immediately from the Aim 1 retention effort (e.g., providers must agree to participate in ECHO to be randomized to Aim 2). The number of sessions of participation within six months of engagement will be the Aim 2 outcome, thus no further efforts on retention will be utilized for the ECHO Nudges study.

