APPENDIX

Table 1: Study Evaluations and Measurements

Type	Name	Time Frame	Brief Description
Primary	Number of recruited providers that contact staff for information about enrolling in the study	From start of recruitment to end of data collection for last participant, up to 1.5 years	Phase 1 recruitment interventions will be compared based on the number of recruited providers that reach out to study staff via email, phone, or any other method.
Secondary	Number of recruited providers that complete enrollment in the study	From start of recruitment to enrollment fulfillment, up to 1 year	Phase 1 recruitment interventions will be compared based on the number of recruited providers that enroll in the study.
Primary	Number of UNC ECHO clinic sessions a participant attends	Study follow up period (from enrollment to 6 months after enrollment; for participants who had not completed as of 3/9/2020 the 6 months was extended by 3 months due to decreased ECHO clinic sessions because of COVID-19)	Phase 2 study interventions will be compared based on the number of UNC ECHO clinic sessions that a participant attends.
Secondary	Total amount of time a participant attends a UNC ECHO clinic session	Study follow up period (from enrollment to 6 months after enrollment; for participants who had not completed as of 3/9/2020 the 6 months was extended by 3 months due to decreased ECHO clinic sessions because of COVID-19)	Phase 2 study interventions will be compared based on the total amount of time that a participant attends a UNC ECHO clinic session (P2)
Secondary	Number of participants that receive a DATA 2000 waiver	Study follow up period (from enrollment to 6 months after enrollment; for participants who had not completed as of 3/9/2020 the 6 months was extended by 3 months due to decreased ECHO clinic sessions because of COVID-19)	Phase 2 study interventions will be compared based on the number of participants that receive a DATA 2000 waiver. MAT waiver training is an 8-hour course for physicians and a 24 hour course for advanced practitioners that is required for providers to prescribe and dispense MAT.

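### Phase 1 randomizes practices, but the Aim 1 provider-level models name no practice-level variance, so standard errors for the contact outcome are too small if colleagues respond alike

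*Combined protocol and SAP*

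**What the plan says.** The Synopsis (Study Design) sets the unit of randomization: "Randomization for this phase will occur at the practice level, as determined by provider address". Section 3.1 agrees: "Primary care providers will be randomized by practice to 1 of 4 study arms". The outcome is counted per person. In Appendix Table 1 the Phase 1 primary outcome reads "Phase 1 recruitment interventions will be compared based on the number of recruited providers that reach out to study staff", and the secondary outcome counts providers who complete enrollment.

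Section 6.1 gives the analysis: "We will use binary models (logit, linear probability models) to examine response to recruitment as a function of study arm". The only adjustment it lists is worded "controlling for provider type and county fixed effects". The Synopsis repeats it. Neither place names a variance estimator, and the document mentions no cluster-robust standard error, GEE, practice random effect, ICC, design effect or number of practices.

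Two other provisions bear on the point. Section 11 allows repeated draws: "the ECHO Nudges study team will randomly select providers in groups of 600 to randomize for pro-social or recruitment as usual invitations". Section 3.4 excludes a provider from Phase 2 if "Another member of the same practice is already enrolled in the study (one provider per practice in Phase 2").

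**The concern.** Providers at one address receive the same letter and share a workplace, a patient population and conversations. If one colleague's response makes another's more likely, 600 providers carry less information than 600 independent observations. A logit or linear probability model with default standard errors does not know this.

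County fixed effects do not repair it. They remove differences between counties, but the letter varies between practices within a county, so correlation inside a practice remains.

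The direction depends on the outcome. For contacting staff, positive correlation makes default standard errors too small and produces too many false positives about the nudge. For enrollment, at most one provider per practice can succeed. That forces negative correlation among mailed colleagues, so default standard errors are too large and the test is conservative. One variance estimator that follows the unit of randomization deals with both.

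**Working it through.** **The plan's own figure.** Section 6.1 claims more than 90% power for a ten-point difference with 600 providers, without stating the baseline rate, alpha or any clustering allowance. I assume two-sided 0.05 and the pro-social main effect, 300 versus 300, with

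power = Φ{[0.10·√n − 1.96·√(2p̄(1−p̄))] / √(p₁(1−p₁)+p₂(1−p₂))}.

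Under independence this gives 98.4% for 5% vs 15%, 93.1% for 10% vs 20%, and 86.7% for 15% vs 25%. The claim is attainable at low response rates if providers are independent.

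**Inputs for the clustering check.**
- Frame: 8087 + 4669 + 4237 = 16,993 providers (Synopsis, Study Rationale), used as N.
- S providers mailed: 600 per group (sections 6.1 and 11).
- Assumed, because the documents do not give them: practice size M of 5, 10, 20 or 50; ICC 0.05 to 0.2, central 0.1; nominal two-sided alpha 0.05.

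**Number of groups.** Aim 2 needs at least 60 enrollees, so groups = 60/(600 × enrollment rate). Assumed rates of 10%, 5% and 2% give 1, 2 and 5 groups.

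**Contact outcome.** Providers are drawn individually, so a mailed provider's expected number of mailed colleagues, counting that provider, is m = 1 + (M−1)(S−1)/(N−1). Then DE = 1 + (m−1)·ICC and true alpha = 2[1 − Φ(1.96/√DE)].

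For example, M = 20 and S = 600 give m = 1 + 19 × 599/16,992 = 1.67. At ICC 0.1, DE = 1.067 and alpha = 2[1 − Φ(1.96/1.033)] = 0.058.

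| Providers per practice | One group | Two groups | Five groups |
|---|---|---|---|
| 5 | 0.052 | 0.053 | 0.058 |
| 10 | 0.054 | 0.057 | 0.069 |
| 20 | 0.058 | 0.066 | 0.090 |
| 50 | 0.070 | 0.091 | 0.151 |

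All entries are at ICC 0.1. Over ICC 0.05 to 0.2, one group gives 0.051–0.053 (M = 5), 0.054–0.066 (M = 20) and 0.060–0.091 (M = 50). Five groups give 0.070–0.129 (M = 20) and 0.102–0.236 (M = 50).

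**Power with one group, 10% vs 20%.** Replacing n by 300/DE gives 91.5% at DE 1.067 (M = 20) and 88.9% at DE 1.173 (M = 50), against 93.1% under independence.

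**Simulation under the null.** Beta-binomial responses, 10% response rate, ICC 0.1, 4,000 runs per case, no county effects. Naive alpha was 0.053, 0.058 and 0.076 for M = 5, 20 and 50 in one group, and 0.097 and 0.154 for M = 20 and 50 in five groups. Practice-clustered standard errors gave 0.049–0.057 in the same cases.

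A separate simulation fixed the number mailed per practice at 2, 3 or 5, with 600 providers and ICC 0.1. Naive alpha was 0.065, 0.074 and 0.102. A practice-level analysis gave 0.052, 0.049 and 0.047.

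**Enrollment outcome (illustrative).** Suppose each provider is willing with probability p = 0.10, k are mailed per practice and at most one enrolls. Then q = [1 − (1−p)^k]/k, ρ = −q/(1−q) and DE = 1 + (k−1)ρ.
- k = 2: q = 0.095, ρ = −0.105, DE = 0.895, naive alpha 0.038.
- k = 3: q = 0.0903, ρ = −0.099, DE = 0.801, naive alpha 0.029.

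The cap also shrinks the letter effect slightly. With k = 2 and 5% vs 10% willing, q is 0.0488 vs 0.0950, so 5.0 points becomes 4.6.

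**The case against.** The strongest reply is that the plan is silent rather than wrong: it names no variance estimator, so clustered standard errors remain possible. That is true, but the models as written default to independence, and leaving the choice until the data are in hand is the weakness.

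The second reply is about size, and much of it stands. In the starting case of one group and small practices, the excess over 5% is a few tenths of a point, hardly visible against Monte Carlo error of about 0.0036. The largest figures need five groups and every practice having 50 providers. Practices of 5 or 10 give 0.058 and 0.069 even with five groups. The simulation also omits county and provider-type adjustment, which could absorb some between-practice variance and lower the residual ICC. In the other direction, section 11 narrows the list below 16,993, which puts more colleagues from one practice in the sample. The enrollment alphas assume exactly two or three mailed in every practice. With m = 1.14 or 1.67 and ρ = −0.105 they would be about 0.048 and 0.042.

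Third, section 11 describes the Aim 1 outcome as the decision to participate. If that means enrollment, the default test is conservative. However, section 3.1 (attempted sign-up) and Table 1 (contact with staff) both place the primary outcome before enrollment.

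Finally, the project is described as a pilot. The Synopsis applies that label specifically to Phase 2, and section 6.1 disclaims power only for Aim 2. For Aim 1 it claims more than 90%.

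**Conclusion.** The concern holds. As written, the Aim 1 models give standard errors that ignore the unit of randomization, and neither the county effects nor the Phase 2 enrollment limit removes within-practice correlation in the contact outcome. Confidence in the omission is high.

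The size cannot be fixed from the documents. At ICC 0.1 it runs from negligible (about 5.2% true type I error with one group and 5-provider practices) to material (9% to 15% with five groups and 20- to 50-provider practices). The likely inflation is modest unless practices are large or several groups are drawn. If only one provider per practice is mailed, there is none. The contact-outcome estimate itself is not claimed to be biased; the issue is its precision. This should be fixed before analysis.

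**What to change.** Add to section 6.1 and the Synopsis: *All Aim 1 models use cluster-robust standard errors (or GEE with robust variance) with practice address as the cluster; a practice keeps one letter assignment across groups of 600.* The second clause is needed because the plan does not say what happens when a later group draws a colleague from a practice already assigned.

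Report the distribution of providers mailed per practice. Optionally, add a practice-level sensitivity analysis of enrollment (any provider enrolled, adjusted for number mailed), keeping the Table 1 provider count as the main outcome.

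The cost is one sentence and one model option, since the practice identifier is already used to randomize. Confidence intervals for contact may widen slightly; those for enrollment may narrow.

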Study Title: Nudges and Incentives to Enhance the Opioid Treatment Workforce

Funder	NIDA
Study Rationale	
Opioid overdoses currently claim the lives of 115 Americans per day. This epidemic is alarming, not just in its effects on the lives of individuals and families, but also on the light it has shined on the disturbing lack of treatment options in many areas. A number of effective treatments are available for opioid use disorder, but many require special training beyond a professional degree. In addition, the complex comorbidities and life circumstances faced by those with an opioid use disorder can deter many providers from investing the time needed to learn how to diagnose and treat individuals needing these services. To date, of North Carolina's 8087 primary care physicians, 4669 nurse practitioners, and 4237 physician assistants, only 785 (<5%) have undergone the waiver training required to provide medication assisted treatment (MAT) for opioid use disorder, a minuscule number of North Carolina's primary care workforce. Many waiver-trained providers are not yet prescribing, due in part to the lack of on-going education or support, so the effective rate of treatment provision is substantially lower than 5%. Further, only one-fifth of NC's zip codes have a waiver-trained provider. ECHO is an evidence-supported hub-and-spoke model of professional development that uses video conferencing technology to bring experts into even the most rural areas to support primary care providers. ECHO for MAT is program in NC that uses the ECHO model to develop a provider workforce that is equipped to provide MAT to those in need of treatment, preventing further accidental deaths from overdose. The time commitment required to develop MAT proficiency can prove to be a barrier to take up since provider time participating in ECHO may represent lost revenue from not seeing patients. This challenge can especially prohibit participation from small and rural practices, often where treatment is most needed. This research project will conduct a pilot study to examine the extent to which informational nudges incorporating specific information from a provider's community into recruitment materials (Aim 1) and financial incentives (Aim 2) affect participation in ECHO MAT by primary care providers. Through these estimates, this study will contribute much-needed information on the incentives that can be used to create a behavioral health workforce that is ready to meet the challenges of the opioid epidemic.

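### Aim 1 randomizes letters by practice, but the planned logit and linear models take no account of practice, so standard errors may be somewhat too small (minor)

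*Combined protocol and SAP*

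**What the plan says.** - **Unit of randomization.** The synopsis (Study Design) states: "Randomization for this phase will occur at the practice level, as determined by provider address". Section 3.1, under Randomization, agrees: "Primary care providers will be randomized by practice to 1 of 4 study arms".
- **Who is in the sample.** Section 6.1 says "we anticipate starting with a random selection of 600 providers from the list of eligible NC providers", so providers are drawn, not practices. The exclusion of a second provider from a practice (synopsis and Section 3.4) is expressly a Phase 2 rule.
- **Analysis.** The synopsis and Section 6.1 share the same sentence: "We will use binary models (logit, linear probability models) to examine response to recruitment as a function of study arm". The adjustment that both of them name is "controlling for provider type and county fixed effects". Neither mentions practice-clustered standard errors, a practice effect, an intraclass correlation or a design effect, and no other section does.
- **Power.** The sample of 600 is one "which gives more than 90% power to detect a ten percentage point difference in the binary outcome, response to study recruitment". No baseline rate, significance level or design effect is given.
- **Later sampling.** Section 11 says "the ECHO Nudges study team will randomly select providers in groups of 600 to randomize for pro-social or recruitment as usual invitations", so the total may exceed 600.

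**The concern.** Everyone sampled from one practice gets the same letter. Colleagues may also share a workload, a manager and an attitude to opioid treatment, and may discuss the invitation. Two of them then carry less information about the letter than two unrelated providers, and a model that treats them as independent overstates precision.

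The county effects do not solve this. They absorb what providers in one county have in common, but the letter varies between practices within a county, and that is the level left unmodeled.

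At stake are the interval and p-value for the Aim 1 primary outcome, the only outcome with a power statement. The problem would grow with each further group of 600, because denser sampling puts more colleagues in the data set.

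**Working it through.** **1. The plan's power figure.** Inputs: 600 providers (Section 6.1) and a 2 x 2 letter design (Section 8), so a two-level letter factor compares about 300 with 300. Two-sided alpha 0.05 and the baseline are assumptions.

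Power = Phi[(d - 1.96 x SE0) / SE1], with SE0 = sqrt(2 p(1-p)/n) at the pooled rate p, and SE1 = sqrt([p1(1-p1) + p2(1-p2)]/n).

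At 10% v 20%: SE0 = sqrt(2 x 0.15 x 0.85/300) = 0.02915 and SE1 = sqrt((0.09 + 0.16)/300) = 0.02887. Then (0.10 - 0.05714)/0.02887 = 1.485, which gives 93.1%.

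Other baselines give 98.4% (5% v 15%), 86.7% (15% v 25%) and 80.9% (20% v 30%). With independent providers, the statement is met for a baseline up to about 12.4%.

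**2. How many colleagues are sampled together.** The synopsis counts "8087 primary care physicians, 4669 nurse practitioners, and 4237 physician assistants", a total of 8087 + 4669 + 4237 = 16,993. Assume practices of m = 5 or 20 and within-practice correlation 0.2. With n providers drawn at random, a sampled provider has on average (m - 1) x n/16,993 sampled colleagues.

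**3. Design effect and naive test.** Design effect DE = 1 + 0.2 x (sampled colleagues). A test that ignores practice rejects under no effect with probability 2 x [1 - Phi(1.96/sqrt(DE))].

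| Providers | m | Sampled colleagues | DE | Naive 5% test rejects |
|---|---|---|---|---|
| 600 | 5 | 4 x 0.0353 = 0.14 | 1.03 | 5.3% |
| 600 | 20 | 19 x 0.0353 = 0.67 | 1.13 | 6.6% |
| 1200 | 5 | 4 x 0.0706 = 0.28 | 1.06 | 5.7% |
| 1200 | 20 | 19 x 0.0706 = 1.34 | 1.27 | 8.2% |
| 2400 | 5 | 4 x 0.1412 = 0.56 | 1.11 | 6.3% |
| 2400 | 20 | 19 x 0.1412 = 2.68 | 1.54 | 11.4% |

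The rows for 1200 and 2400 assume that a practice keeps its letter across groups.

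**4. Simulation.** With the same practice sizes and correlation, and 50 or 100 assumed counties fitted as fixed effects:

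- The unclustered test rejects 5-7% under no effect at 600 providers, 6-9% at 1200 and 5-12% at 2400.
- Practice clustering with a finite-sample correction gives 4-6%.
- Clustering without the correction gives 6-7% at 600. In one run with practices of 20 and 100 counties it gave 7.3-7.9%, worse than not clustering (5.6-5.9%), while the corrected version gave 5.3-5.7%. The correction is therefore needed.

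**5. Power with practice allowed for.** Replacing n by n/DE in step 1 at 10% v 20% gives 92.5% (DE 1.028) and 89.9% (DE 1.134). Simulated power, which also pays for the county effects and the correction, is about 84-92%.

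**6. Side check on the logit, illustrative only.** Suppose the county effects are dummies fitted by ordinary maximum likelihood and an odds ratio is reported. With 600 independent providers at 5% v 15%, the true odds ratio is (0.15/0.85)/(0.05/0.95) = 3.35. The median estimate is 3.56, 3.73 and 3.99 with 25, 50 and 100 assumed counties. Over the response rates tried, the log odds ratio is too far from zero by roughly 4-18% for unequally sized counties, and by about 21% in an extreme case of 100 near-equal ones. With no effect the median odds ratio is 0.98-1.01. A conditional logit is 1-3% high, and the linear model is within 1.5% of the true difference.

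**The case against.** **The size is assumed, and it is small where the plan is explicit.** This stands. Practice size and correlation are not in the documents, and 600 is the only total that Section 6.1 states. There the naive test is at most about two points above nominal. The figure of about 12% needs 2400 providers, large practices, a correlation of 0.2 and letters that stay with the practice across groups; Section 11 does not settle the last of these.

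**Correlation may be lower, or of another sign, for enrollment.** This stands in part. With one enrollee per practice, colleagues' enrollment cannot be positively correlated in the way assumed. But the primary measure in Appendix Table 1 is contact with staff, which that rule does not limit.

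**The 16,993 pool is the whole workforce, not the eligible list.** This is true, but a shorter list means a larger sampled fraction and hence a larger design effect.

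**A reader might infer that the Aim 1 odds ratio will be exaggerated.** The documents do not support that. County fixed effects can equally mean a conditional logit, the plan never says that an odds ratio is the reported effect, the planned linear model is free of the problem, and there is no shift under no effect. The plan does leave open which model and scale come first. That is a specification choice and not an error in either model.

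**A reader might also infer that the power statement is wrong.** It is not shown to be. It is attainable at low baselines, but it omits the baseline and design effect on which it rests.

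**Conclusion.** The point holds as a minor gap: the analysis omits the unit that was randomized. That reading rests on the text alone. Its numerical effect rests on assumed practices of 5-20, a correlation of 0.2 and 50-100 counties: about 5-7% rejection for a nominal 5% test at 600 providers, and up to about 12% at 2400 if practices keep their letter. If colleagues' responses are uncorrelated, there is no inflation. The odds-ratio shift is a conditional side note and does not carry the finding.

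**What to change.** In Section 6.1 and the synopsis:

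1. State that standard errors of the Aim 1 models are clustered by practice, across all groups of 600 mailed, with a finite-sample correction that counts the county effects.
2. Qualify the power statement with its assumed baseline and design effect.
3. If an odds ratio is reported, obtain it from a conditional logit stratified by county. Otherwise report the percentage-point difference over all providers, which is the scale of the power statement.

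This is a change of wording that uses standard software and needs no new outcome data; practice is already identified from the provider's address for randomization. The cost is slightly wider intervals and slightly lower power: about 84-92% at 600 providers for an assumed 10% v 20% on a two-level letter factor, so the claim of more than 90% may not be met. A conditional logit would still learn nothing from counties without a responder.
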